Pearson's chi-squared test will be used to evaluate the treatment difference between treatment groups for the categorical response endpoints. The continuous response endpoints will be analyzed using the 2-sample t-test. The time-to-event endpoints will be analyzed using the log-rank test. Kaplan-Meier curves will also be presented.

Additional exploratory analyses will be performed as appropriate. Such analyses may include logistic regression model, analysis of variance model, and/or mixed-effects model. Subgroup analyses based on demographics, baseline characteristics, study compliance, etc, will also be performed.

Sample Size Justification:

Formal sample size calculations were not performed. The sample size is based on recent literature of comparative studies in sarcoidosis.

Date of Issue: 13 May 2020

SUMMARY OF CHANGES

The summary of changes presented below reflects the changes made in Version 2 Amendment 1. Formatting, consistency, and minor editorial changes are not included.

The primary reason for Version 2 Amendment 1 is to extend this product's and this study's treatment to countries other than the US, as currently Acthar Gel is only approved in the US. Additionally, updates or revisions are established for: study design that is revised to exploratory, changing enrollment and study duration timelines, adding WPAI questionnaire for collection of data for health economics and outcomes research, adding provisions for remote collection of data for those extenuating occasions when visits cannot be made in person, adding diary training and reviews, adding monitoring for possible allergic reactions to the first dose of Acthar Gel in the Open-label Extension Phase, removing an additional definition for SAEs that are not part of the standard definitions, and adding corticosteroid tapering for subjects entering the open label study period. Further detail is presented in [Appendix 1](#).

TABLE OF CONTENTS

1.	TITLE PAGE	1
	SPONSOR SIGNATURE PAGE.....	2
	ACKNOWLEDGEMENT OF RECEIPT AND UNDERSTANDING OF SPONSOR STUDY MATERIALS	2
2.	SYNOPSIS.....	4
	SUMMARY OF CHANGES	13
3.	ABBREVIATIONS	20
4.	STUDY SCHEMATIC AND SCHEDULE OF EVENTS	22
4.1.	Study Schematic.....	22
4.2.	Schedule of Study Events	22
5.	ETHICAL CONSIDERATIONS	27
5.1.	Institutional Review Board/Independent Ethics Committee.....	27
5.2.	Ethical Conduct of the Study	27
5.3.	Subject Information and Consent.....	27
6.	BACKGROUND INFORMATION AND RATIONALE	29
6.1.	Sarcoidosis Overview.....	29

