7.3. Efficacy Endpoints

The endpoints for the efficacy objective are:

- STS response rate at 24 weeks (Visit 8).
- STS response rate at 48 weeks (Visit 11).
- Physician and subject independent responses to the question “Would you choose to continue current treatment?” at 24 and 48 weeks.
- Time to response as evaluated at earlier time points (Weeks 4 to 20) as determined by the investigator based on clinical judgment and the following parameters:
 - Patient reported outcomes.
 - Corticosteroid tapering.
 - Patient Global Assessment.
 - Physician Global Assessment
 - PFT (at applicable time points).
 - ePOST.
 - Supportive efficacy endpoints per applicable time points.
 - 6MWT.
 - Symptom relief (Leicester Cough Questionnaire, Medical Research Council Dyspnea Scale, steroid toxicity questionnaire).
 - CXR - change in Scadding score.

- Percentage change in overall DLCO.
- Percentage of subjects with improvement in DLCO of $\geq 5\%$; $\geq 10\%$; and $\geq 15\%$.
- Percentage change in overall forced vital capacity (FVC).
- Percentage of subjects with improvement in FVC of $\geq 5\%$, $\geq 10\%$, and $\geq 15\%$.
- Percentage of improved/stable/deteriorate side-by-side comparison of HRCT on a 5-point Likert score: much worse; worse; unchanged; better; much better (central reader).
- Percentage of improved/stable/deteriorated side-by-side comparison of CXRs on a 5-point Likert score: much worse; worse; unchanged; better; much better (central reader).
- Percentage change in Scadding Score (side-by-side comparison of CXRs by a central reader, [Scadding, 1961](#)).
- Percentage change in patient-reported outcomes and symptom questionnaires.
- Percentage failed corticosteroid taper.
- Time to failed corticosteroid taper (for subjects failing taper).
- Change from baseline in WPAI over time.

Biomarkers

Biomarker levels will be compared between Screening, and every 12 weeks (up to 48 weeks for those subjects participating in the optional Open-label Extension Phase). Serum aliquots will be kept for each of these time points. Possible biomarkers include angiotensinogen, sIL-2R and vitamin D 1,25. The final selection of biomarkers will be made based on the scientific knowledge and emerging guidance closer to the completion of the study.

The genomic profile (optional) will be assessed based on the understanding of genetic factors at the time of study completion.

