15.5. Efficacy Analysis

Efficacy analyses will be performed on the mITT Population. All efficacy endpoints will be summarized and analyzed. Pearson's chi-squared test will be used to evaluate the treatment difference between treatment groups for the categorical response endpoints. The continuous response endpoints will be analyzed using 2-sample t-test. The time-to-event endpoints will be analyzed using log-rank test. Kaplan-Meier curves will also be presented.

Additional exploratory analyses will be performed as appropriate. Such analyses may include logistic regression model, analysis of variance model, and/or mixed-effects model. Subgroup analyses based on demographics, baseline characteristics, study compliance, etc, will also be performed.

Missing data imputations will be performed as appropriate. In general, the last-observation-carried-forward method will be used to impute missing data. Additional missing data imputation may be performed as needed.

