8.3.2. Treatment Compliance

During each visit, the number of injections that a subject was expected to take and the number of injections that a subject actually took since previous visit until prior to the current visit will be recorded on the eCRF.

Treatment compliance (%) of double-blind treatment phase is defined as:

$$\frac{(\text{Number of injections taken during double - blind treatment phase}) \times 100}{\text{Number of injections expected to be taken during double - blind treatment phase}}$$

Treatment compliance (%) of open-label extension phase is defined as:

$$\frac{(\text{Number of injections taken during the duration open - label extension phase }) \times 100}{\text{Number of injections expected to be taken during open - label extension phase}}$$

The study drug compliance rate in the double-blind treatment phase, and compliance rate in the open-label extension phase will be summarized by treatment group using the descriptive statistics. The compliance rates will also be summarized by categories (<80, 80 to <=120, and >120).

9. Efficacy Analysis

All efficacy evaluations will be conducted using the mITT population unless otherwise specified and will be provided by treatment group for the double-blind treatment phase. Efficacy evaluations will only be summarized descriptively using the open-label safety population by treatment group and total for the open-label extension phase. All summaries and analyses will be conducted on the observed values unless otherwise specified. All efficacy data will be presented in listings based on the mITT population in the double-blind treatment phase and based on the open-label safety population in the open-label extension phase. The derived efficacy variables will be displayed in data listings as well.

Additional subgroup analyses by sex, race and ethnicity will be performed on missing imputed data as specified. Other exploratory analyses may be performed as appropriate.

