vs. non-responder rate. At 48 weeks (Visit 11) during open-label phase, the proportions of STS responder and non-responder along with 95% CI will be provided. The 95% CI will be calculated by using the exact (Clopper-Pearson) method.

Missing STS scores will be imputed at 24 weeks (Visit 8) during double-blind treatment phase. Last observation carried forward (LOCF) method will be employed to impute missing component(s) if any component of STS is missing at the post-baseline visit during double-blind treatment phase. If there is still missing component(s) after applying LOCF imputation method, STS score will remain as missing. Subjects who do not provide data (after component level LOCF imputation) to allow classification as responders will be considered non-responders, that is, missing data will be imputed as non-responder. The same missing data imputation method will be applied to other similar efficacy endpoints in double-blind treatment phase. No imputation will be applied to the open-label extension phase. A bar plot of STS category will be provided at 24 weeks (Visit 8) during double-blind treatment phase and at 48 weeks (Visit 11) during open-label phase, respectively.

Sensitivity analyses with using only the observed data will be performed for the above analysis at 24 Weeks (visit 8) only.

Subgroup analyses by sex, race and ethnicity will be performed in similar manner as specified above on the imputed data only.

STS component scores including FVC % Predicted Score, DLCO % predicted Score, HRCT Score, King's Sarcoidosis Questionnaire (KSQ) General Health Score, Fatigue Assessment Score and Corticosteroid Taper Score will be summarized. Number and percentage of subjects in each category (Improved, Unchanged and Deteriorate) of each STS component score presented in Table 1 will be provided at 24 weeks (Visit 8) and at 48 weeks (Visit 11). Pearson's chi-square test (or Fisher's exact test if any expected count is less than 5) will be used to assess the comparability between treatment groups for each STS component at 24 Weeks (visit 8) only.

Listings of STS components and STS scores will be provided by study phases. Subjects with any missing component of STS will be indicated.

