9.8. Corticosteroid Tapering

The number and percentage of subjects who have dose adjustment and justifications for dose change will be summarized at each scheduled visit by treatment group and study phase. Descriptive statistics will be provided for doses and doses change from baseline at each scheduled visit. All corticosteroid dose will be converted to prednisone equivalent dose. Additionally, weekly average prednisone or equivalent daily dose (mg/day) will be calculated from prior and concomitant medication data for prednisone collected prior to week 4 (Visit 3) and post week 48 (Visit 11) and corticosteroid use data collected between week 4 (Visit 3) and week 48 (Visit 11). The average weekly daily dose change and percent change from baseline, and change and percent change from baseline of active treatment to week (from week 25 to week 48 in open-label phase only) will be summarized descriptively by weeks from week 1 to week 24 in double-blind phase and from 25 to week 48 in open-label phase. The line plots of mean (+/- standard error) percent change of average weekly daily dose from baseline by weeks will be provided for double-blind treatment phase and overall study phase.

Subjects whose corticosteroid dosage increased for more than 2 weeks will be considered as failing to corticosteroid taper. Pearson's chi-square test (or Fisher's exact test if any expected count is less than 5) will be used to compare the treatment difference between treatment groups for the percentage of subjects who fail corticosteroid taper in double-blind treatment phase only.

Time to failing corticosteroid taper is defined as:

Time to failing corticosteroid taper (day) = date of failing corticosteroid taper - date of first dose + 1.

Time to failing corticosteroid taper will be summarized by descriptive statistics by treatment group for subjects who fail corticosteroid taper.

A listing will be provided for the corticosteroid use by subject and visit.

10. Safety Analysis

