11.2. Genetic Profile

Genetic sample obtained for subjects who has signed the genetic inform consent form at study entry may be explored and presented in tables. Descriptive statistics will be provided if data is available.

All genetic data will be presented in a listing.

12. Interim Analysis

No formal interim analysis is planned.

13. Changes in the Planned Analysis

The summary of changes presented below reflects the changes in the planned analysis described in protocol:

- The protocol planned endpoint analysis for “Change from baseline in WPAI over time” will not be performed given very few subjects have taken WPAI questionnaire. WPAI data will be only presented in listings.
- The protocol planned endpoint analysis for “Time to response (TTR) as evaluated at earlier time points (Weeks 4 to 20) as determined by the investigator based on clinical judgment” will not be performed.
- The protocol planned analysis for biomarker and genetic endpoints may not be performed depending on the availability of the data.

14. References

Judson MA. Advances in the diagnosis and treatment of sarcoidosis. *F1000Prime Reports* 2014; 6: 89.

Mallinckrodt ARD, Inc. A Phase 4 Multicenter, Randomized, Double Blind, Placebo Controlled Pilot Study to Assess the Efficacy and Safety of H.P. Acthar® Gel in Subjects with Pulmonary Sarcoidosis. Original, 06 October 2017.

15.Appendices

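### Time to failed corticosteroid taper: the protocol's log-rank test and Kaplan-Meier curves are absent from the SAP without being declared, and the failers-only summary that replaces them has no censoring and no defined failure date

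*SAP*

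**What the plan says.** **Method in the protocol.** Protocol 15.5 states: "The time-to-event endpoints will be analyzed using log-rank test. Kaplan-Meier curves will also be presented". The Statistical Methods part of the synopsis says the same.

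**Endpoint in the protocol.** Protocol 7.3 lists "Time to failed corticosteroid taper (for subjects failing taper)". The synopsis and SAP 3.2.1 carry the same restriction to failers.

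**Analysis in the SAP.** SAP 9.8 defines the event: "Subjects whose corticosteroid dosage increased for more than 2 weeks will be considered as failing to corticosteroid taper". Time runs from first dose to a date of failing, plus one day, but the date of failing is not defined. The analysis is: "Time to failing corticosteroid taper will be summarized by descriptive statistics by treatment group for subjects who fail corticosteroid taper". A chi-square or Fisher test is kept for the percentage failing in the double-blind phase. The SAP contains no log-rank test, Kaplan-Meier curve or censoring rule, and the SAS code in SAP 15.4 covers only the t-test, chi-square, Fisher and MMRM.

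**Declared changes.** SAP 13 opens with "The summary of changes presented below reflects the changes in the planned analysis described in protocol" and lists three items: WPAI, time to response, and the biomarker and genetic endpoints. Time to failed taper is not among them.

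**Missing data.** The opening of SAP 9 says "All summaries and analyses will be conducted on the observed values unless otherwise specified". SAP 9.1, after describing component-level LOCF followed by non-responder imputation, adds "The same missing data imputation method will be applied to other similar efficacy endpoints in double-blind treatment phase".

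**The concern.** Two protocol endpoints are worded as times. SAP 13 drops time to response and says so. Time to failed taper is then the only one left, and it loses its planned method without comment, so the SAP holds no survival analysis at all.

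What remains cannot compare the arms. Whether a subject fails is itself an outcome of treatment, so the failers in each arm are not comparable groups. An effective drug mainly reduces how many subjects fail and barely moves the mean time among those who do. Subjects who leave early without failing drop out of the table altogether.

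The calculation is also not reproducible as written. The date of failing could be the first day of the increase or the day it passes 2 weeks. SAP 9.8 gives no minimum increase and no reference dose, whereas the STS taper item in SAP Table 1 requires at least 5 mg. An increase still running at Visit 8 has no stated phase.

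**Working it through.** The documents give no failure rate, dropout rate or power for this endpoint, so there is no plan figure to reproduce. Inputs from the documents: 55 randomised (SAP 4.1), 1:1 allocation (SAP 4.2), 24 double-blind weeks (SAP 3.1), two-sided 0.05 (SAP 4.3). All failure and dropout rates below are assumptions. Failure and dropout times are exponential with 28 v 27 subjects unless stated. Percentages are 24-week cumulative probabilities, and simulations use 10,000 trials per scenario.

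**1. What the failers-only mean can show.** With cumulative failure p, the hazard is λ = −ln(1−p)/24, and the mean time among failers is 1/λ − 24(1−p)/p.

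- p = 0.30: 67.29 − 24 × 0.70/0.30 = 67.29 − 56.00 = 11.29 weeks
- p = 0.60: 26.19 − 24 × 0.40/0.60 = 26.19 − 16.00 = 10.19 weeks

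Halving the failure percentage moves the mean by 1.1 weeks. In simulation the better arm has the shorter mean in about 35-37% of trials. For 20% v 50% the means are 11.55 v 10.62 weeks, with the wrong order in about 40%. If failure is possible only from Week 4, when tapering starts (Protocol 10.1), the 30% v 60% means are 13.4 v 12.5 weeks, with the wrong order in 36%.

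The mean also depends on follow-up. With the same hazard throughout (35% failing by Week 24) and dropout of 0%, 20% or 40%, spread uniformly over the phase, it is 77.9, 74.8 or 71.3 days.

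**2. The undefined date.** Onset and the day the increase passes 2 weeks differ by about 14 days, or 14/168 = 8.3% of the phase. Halving the hazard from placebo failure of 20%, 35% or 50% moves the failers-only mean by 1.5, 3.0 or 4.8 days (80.9 to 82.4, 78.0 to 81.0, 74.4 to 79.2). Applied consistently, the choice shifts both arms alike, but it changes every reported time and decides which late increases count.

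**3. What log-rank adds in power.**

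| Failing, Acthar v placebo | Dropout | Log-rank | Percent-failed test (leavers not failed) |
|---|---|---|---|
| 30% v 60% | none | 64% | 65% |
| 20% v 50% | none | 66% | 67% |
| 30% v 60% | 30% in both arms | 57% | 55% |

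These are large effects: 30% v 60% is a hazard ratio of ln 0.70/ln 0.40 = 0.39. At a hazard ratio of 0.5, placebo failure of 20%, 35% or 50% gives about 8, 15 or 22 events. With power Φ(√d × |ln 0.5|/2 − 1.96), log-rank then has about 17%, 27% or 37% power; 80% would need 66 events.

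**4. Early leavers in the percent-failed test.** Take no true effect, 60% failing in both arms, and an extreme assumed contrast of 37% v 10% dropout, independent of failure. The 37% is the early-stop figure Protocol 6.1 prints for a retrospective chart review in which 4 of 18 stops were for cost; the 10% is assumed.

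- *Leavers count as not failed.* The expected percentage is a/(a+b) × [1 − 0.4(1−d)], with a = −ln 0.4 and b = −ln(1−d). This gives 49.7% v 57.4%, a false 7.7 points in favour of Acthar. The test rejects in about 10% of trials.
- *Leavers count as failed.* The expected percentage is 1 − 0.4(1−d): 1 − 0.4 × 0.63 = 74.8% v 1 − 0.4 × 0.90 = 64.0%, a false 10.8 points against Acthar. The test rejects in about 13-14% of trials, nearly all against Acthar.

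Log-rank with censoring stays near 5%. At 20% v 10% dropout, with leavers not failed, the percent-failed test rejects in about 6%. If dropout is correlated with failure (Gaussian copula 0.8), log-rank at 37% v 10% is inflated too: 7.0% with 60% failing and 9.4% with 40% failing.

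**The case against.** **The SAP follows the protocol's endpoint.** Protocol 7.3 limits this endpoint to failers and SAP 9.8 implements that. Protocol 15.1 calls its methods a general description and leaves detail to the SAP. On this view log-rank was meant for time to response, whose removal is declared. This stands in part: the conflict starts inside the protocol. But Protocol 15.5 speaks of time-to-event endpoints in the plural, log-rank needs the non-failers in the risk set, and dropping a named method is not added detail. SAP 13 was the place to say so.

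**The gain is small.** This also stands. The failers-only summary carries no test, the percent-failed test and the weekly dose summaries remain, and log-rank adds no power without dropout. The 35-37% wrong-order figure partly reflects sampling noise with few failers in an untested table; the expected means do go the right way.

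**Leavers are partly followed.** Protocol 11.10 asks for Visit 8 procedures and a follow-up visit after early termination, and steroid data run to Week 48. A late increase is therefore recorded; what is missing is how it is classified.

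Three stronger readings are not supported. A reader might infer that the percent-failed test favours Acthar. That depends on leavers counting as not failed, which the opening of SAP 9 suggests. SAP 9.1, with SAP 9.2, 9.3 and 9.4.1, suggests the unfavourable outcome instead, and the distortion then runs the other way. A reader might also infer from the heading of Protocol 15.8 that the study report need not mention the change; its text covers departures from the planned analysis and can include the protocol's plan. Nor do the documents show why the method was dropped.

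**Conclusion.** The point holds as a minor-to-moderate issue on one endpoint of an exploratory study. The mismatch of method, the missing SAP 13 entry, the absent censoring rule and the undefined failure date are read directly from the documents and rest on no assumption. That the failers-only summary is nearly uninformative follows from its construction; the figures of 11.3 v 10.2 weeks and 35-37% rest on assumed failure rates and exponential times.

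The case for the protocol's method is a usable time-to-event estimate that keeps every mITT subject and handles early leavers, not extra power. With 55 subjects the log-rank result will be imprecise, and it assumes that dropout is unrelated to failure. Distortion of the percent-failed test is clear only under strongly unequal dropout, and no direction should be asserted until the rule for leavers is stated. The tapering algorithm announced in Protocol 7.2.4 is not visible in the available text, so it may say more about worsening than can be seen here.

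**What to change.** In SAP 9.8:

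- Analyse time to first taper failure in the double-blind phase for all mITT subjects, under the SAP's existing treatment-assignment rule. Censor unfailed subjects at the last double-blind steroid record or Visit 8. Present Kaplan-Meier curves and the log-rank test as Protocol 15.5 states.
- Define the failure date (onset, or the day the increase exceeds 2 weeks) and the phase to which an increase still running at Visit 8 belongs.
- Reconcile the failure event, which has no minimum increase or reference dose, with the STS taper item in SAP Table 1.
- State how leavers without an observed failure count in the percent-failed test.
- Keep the failers-only table, labelled as descriptive.

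In SAP 13, record how the failers-only endpoint wording (protocol synopsis, Protocol 7.3, SAP 3.2.1) is reconciled with Protocol 15.5. Because censoring assumes uninformative dropout, a sensitivity analysis counting withdrawal for lack of efficacy as failure is a reasonable option; SAP 5 already categorises that reason.

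The cost is a few sentences, one SAP 13 entry and one standard SAS procedure. No new data are needed: SAP 9.8 already uses the corticosteroid-use records from Week 4 to Week 48, and Protocol 10 records concomitant medication through follow-up.

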10.1. Adverse Events

An AE is any untoward or undesirable medical occurrence in a subject who is administered an IMP, which does not necessarily have to have a causal relationship with this treatment.

A TEAE is defined as an event that begins or worsens on or after the start of study drug through 30 days after the date of the last dose. The first dose of IMP at the open-label extension phase will be used as cutoff date, the TEAEs started before the cutoff date will be summarized in the double-blind treatment phase and the TEAEs started on or after the cutoff date will be summarized in the open-label extension phase; Subjects who did not continue into the open-label extension phase will be summarized in the double-blind treatment phase only.

If a subject experiences the same AE more than once with different severity, then the event with the highest severity level will be tabulated in “by severity” tables. If a subject experiences the same AE more than once with different relationship to study drug, then the event with the most related level will be tabulated in “by relationship” tables. Note that AEs with a missing severity will be considered as severe, and AEs with missing relationship will be considered as related to study drug. Adverse events are considered treatment-related if the relationship to study drug is possibly related, related or missing.

The incidence of AEs will be summarized in tables with the number and percentage of subjects with AEs by SOC and PT. At each level of SOC or PT, a subject with multiple events will only be counted once per SOC or PT. Percentages of subjects with AEs will be calculated out of the number of subjects in the safety population. SOC will be presented alphabetically and PTs within each SOC will be presented in decreasing order of frequency based on the total number of subjects with each AE in the Acthar group. The following categories of TEAE will be summarized by SOC and PT by treatment group and total for the double-blind treatment phase and the open-label extension phase separately:

- TEAEs
- TEAEs by severity (Mild, Moderate, and Severe)
- TEAEs by relationship (Not Related, Unlikely Related, Possibly Related, and Related)
- Treatment related TEAEs
- Serious TEAEs
- Serious TEAEs by relationship (Not Related, Unlikely Related, Possibly Related, and Related)
- TEAEs leading to study drug discontinuation
- TEAEs leading to death

Overview tables of the above categories will also be provided.

All AEs will be presented in a data listing by study phase and TEAEs will be flagged in the listing.

